### 6.2.2 Treatment Delay

Clinical judgment will be used to determine appropriate management of the subject experiencing any adverse event (AE). The suggested criteria for dose modification for tivozanib hydrochloride drug-related AEs are summarized in the table below.

**Table 3. Tivozanib Hydrochloride Dose Modification Guidelines for Drug-Related Adverse Events**

Drug-Related Adverse Events (excluding Hypertension  )	Action Taken	Subsequent Dosing Modification
Grade 1	No dose interruption, or reduction required; adverse event management is at the discretion of the Investigator	None required; Dosing may continue at the same dose
Grade 2	No dose interruption, or reduction required; adverse event management is at the discretion of the Investigator	None required; Dosing may continue at the same dose
Grade 3	Interrupt dosing until toxicity resolves to grade $\leq 1$	Dosing may resume at reduced dose (see below for dose reduction guidelines)
Grade 4	Interrupt dosing until toxicity resolves to grade $\leq 1$ .	Dosing may resume at reduced dose (see below for dose reduction guidelines).

1 Hypertension must be treated as described in Section 6.2.5 prior to any dose modification

### 6.2.3 Tivozanib Hydrochloride Dose Interruption

Subjects with drug related Grade 3/4 AEs should have their dose interrupted to allow for resolution of toxicities to grade  $\leq 1$ . The exception is HTN, which must first, be treated as described in **Section 6.2.5** prior to any dose modification. Dosing interruptions of  $\leq 2$  weeks will be allowed. Upon resolution of toxicities to  $\leq$  grade 1, dosing may resume at one dose level below the current dose, based on the Investigator's discretion for an individual subject's safety and tolerability. Doses missed during a drug interruption are not to be made up. If dosing is interrupted for  $> 2$  weeks, dosing should be discontinued, unless there is clear benefit from treatment.

### 6.2.4 Tivozanib Hydrochloride Dose Reduction

Dose reductions of tivozanib by 0.5 mg/day will be required for patients with  $\geq$  Grade 3 drug-related adverse events. This excludes grade  $\geq 3$  hypertension, nausea, vomiting, and diarrhea, without adequate supportive care. Hypertension, nausea, vomiting, and diarrhea may resume at the same dose level after adequate supportive care, in the investigators opinion it is safe to proceed at the same dose level. If hypertension, diarrhea, nausea, and vomiting recurs despite adequate supportive care tivozanib must be dose reduced, up to 2 dose reductions are allowed. Once a patient's dose of tivozanib is reduced, it may not be re-escalated through the

remainder of the patient's participation in the study. 1 mg capsules every other day for 10 doses will be used, as 0.5 mg capsules are no longer manufactured. According to the drug manufacturer AVEO Pharmaceuticals, this dosing regimen will achieve comparable exposure to 0.5 mg QD, based on the half-life of Tivozanib.

### 6.2.5 Management of Hypertension

Hypertension (HTN) that occurs during study treatment must be treated with anti-hypertensive drugs prior to any dose reduction. Recommended management of HTN for subjects receiving study drug is presented in **Appendix C** and **Appendix D**.

Persistent HTN is defined as 2 consecutive elevated blood pressure (BP) measurements preferably taken in the clinic and obtained at least 1 hour apart. It is recommended that 24-48 hours should elapse between the decision steps. For a listing of recommended DHP (dihydropyridine) calcium channel blockers, angiotensin converting enzyme (ACE) inhibitors, and angiotensin receptor blockers, see **Appendix D**, Recommended Anti-hypertensive Medications. **Note:** If a subject has controlled HTN on an anti-hypertensive regimen at baseline and then develops a worsening of HTN requiring more intensive therapy than the previous regimen, this would be considered Grade 3 HTN.

### 6.3 General Concomitant Medication and Supportive Care

Agents known to be Cytochrome P450 (CYP3A4) strong inhibitors and inducers must be avoided for the duration of tivozanib treatment. Appropriate replacement drugs will be prescribed with the help of clinical Pharmacist. An individual patient's risk/benefit should be taken into account when administration of a CYP3A4 inhibitor or inducer is required as these agents may decrease serum concentrations of tivozanib, potentially impairing efficacy. For a complete list and additional information, refer to the following website: <http://medicine.iupui.edu/clinpharm/ddis/table.aspx>.

Since there is a potential for interaction of tivozanib with other concomitantly administered drugs through the CYP3A4 system, the electronic case report form (eCRF) must capture the concurrent use of all other drugs, over-the-counter medications, or alternative therapies. The Investigator should be alerted if the patient is taking any agent known to affect or with the potential to affect selected CYP450 inhibitors and inducers.

Patients may be pretreated for nausea and vomiting with appropriate anti-emetics.

### 6.4 Treatment Discontinuation

Patients with non-hematologic Grade 4 drug related adverse events will permanently discontinue study drug unless the patient has experienced objective evidence of benefit and the investigator has determined that it is reasonably safe to continue treatment despite the occurrence of a life threatening adverse event. If a patient has dose interruption  $\leq 2$  weeks from the next scheduled dose, missed doses will not be made up (i.e., cycle duration will remain unchanged). If any drug-related toxicity results in interruption of dosing of  $> 2$  weeks from the next scheduled dose, the subject should be discontinued from tivozanib, unless there is clear benefit from treatment.

Upon treatment discontinuation, all end of study evaluations and tests will be conducted. All subjects who discontinue due to an AE must be followed until the event resolves or stabilizes. Appropriate medical care should be provided until signs and symptoms have abated, stabilized, or until abnormal laboratory findings have returned to acceptable or pre-study limits. The final status of the AE will be reported in the subject's medical records and the appropriate eCRF.

Reasons for treatment discontinuation should be classified as follows:

- Death
- Progressive disease
- Treatment-related toxicity
- Toxicity unrelated to treatment
- Investigator judgment
  - The Investigator may withdraw a subject if, in his/her judgment, it is in the subject's best interest to do so.
- Noncompliance
- Subject voluntary withdrawal
  - A subject may withdraw from the study at any time, for any reason. If a subject discontinues treatment, an attempt should be made to obtain information regarding the reason for withdrawal.
- Early withdrawal of subject(s)
- Sponsor decision.

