## 6.2 Dose Modifications

### 6.2.1 Definition of Dose-Limiting Toxicity

A DLT is any Grade 3 or higher toxicity that is possible, probable, or definitely related to study drug.

Management and dose modifications associated with the above AEs are outlined in the below sections. Dose level will be, considered tolerable following completion of 1st cycle of treatment.

Patients who experience a DLT will be dose reduced to the next lower dose cohort for continuation on the study.

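### Dosing text is inconsistent in three places: reduce versus stop after non-hematologic Grade 4 toxicity, two reductions where the 1 mg dose allows one, and a daily instruction in the alternate-day diary

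*Combined protocol and SAP*

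**What the plan says.** **Severe toxicity.** Section 6.4: "Patients with non-hematologic Grade 4 drug related adverse events will permanently discontinue study drug unless the patient has experienced objective evidence of benefit". The exception has a second condition: the investigator must also judge it reasonably safe to go on. Section 6.2.4: "Dose reductions of tivozanib by 0.5 mg/day will be required for patients with" drug-related events of Grade 3 or higher, leaving out hypertension, nausea, vomiting and diarrhea that have not yet had adequate supportive care. Those four "may resume at the same dose level after adequate supportive care" if the investigator thinks it safe. Section 6.2.1 defines a DLT as any related toxicity of Grade 3 or above and adds: "Patients who experience a DLT will be dose reduced to the next lower dose cohort for continuation on the study".

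The remaining dose-modification text is permissive. Section 6.2.2: "The suggested criteria for dose modification for tivozanib hydrochloride drug-related AEs are summarized in the table below". Table 3, in both its Grade 3 and its Grade 4 row: "Dosing may resume at reduced dose (see below for dose reduction guidelines"). Section 6.2.3: "dosing may resume at one dose level below the current dose".

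**Number of reductions.** If one of the four named events recurs despite supportive care, Section 6.2.4 says "tivozanib must be dose reduced, up to 2 dose reductions are allowed". Section 3.3.1 fixes 1 mg daily as the Phase 2 dose. Section 5.1 supplies 1 mg capsules, and Section 6.1 limits each dose to one capsule. The footnote to Table 2 says that the 0.5 mg strength is not manufactured. Sections 3.3.3, 6.1 and 6.2.4 give the reduced regimen as 1 mg on alternate days for 10 doses.

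**Diary.** The introductory text of the dose-reduced diary (Appendix F2) tells the patient to take the medication each morning, daily. The full-dose diary (Appendix E1) has the same sentence. The grid in Appendix F2 numbers doses 1 to 10 on Days 1, 3, ..., 19 and crosses out the even days through Day 20.

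**The concern.** These are operative rules for patients with limited liver reserve, applied at several sites, and one of them is read directly by patients.

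- A site that applies 6.2.4 literally would reduce the dose and continue after a life-threatening, drug-related, non-hematologic event, where 6.4 would end treatment.
- A patient already on the reduced regimen who has another event calling for a reduction has no expressly stated next step.
- A reduced patient who follows the diary sentence goes back to the daily dose from which he or she was reduced for toxicity.

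The stakes are patient safety and uniform dosing across sites.

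**Working it through.** The plan gives no figure of its own for this point. The check is a comparison of texts plus counting.

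**1. Reduce or stop.** The two mandatory rules, by type of drug-related event:

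| Event | Section 6.4, Grade 4 rule | Section 6.2.4 | Result |
|---|---|---|---|
| Grade 3 (outside the four named events) | does not apply | reduce | consistent |
| Grade 4, hematologic | does not apply | reduce | consistent |
| Grade 4, non-hematologic, both exception conditions met | may continue | reduce | consistent |
| Grade 4, non-hematologic, exception not met (outside the four named events) | stop permanently | reduce | opposite |

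The conflict is confined to the last row. Section 6.2.1 gives the same instruction as 6.2.4, but its reference to a lower dose cohort is dose-escalation language and may be meant for Phase 1b only. In Phase 2 the conflict therefore rests mainly on 6.2.4. Table 3 and Section 6.2.3 only permit resumption, so they do not strictly contradict 6.4, although neither mentions it. The same-dose sentence for the four named events sets no upper grade and does not mention 6.4 either.

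**2. Available reductions in steps of 0.5 mg/day** (levels from Table 2: 0.5, 1 and 1.5 mg).

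- From 1.5 mg: 1.5 → 1.0 → 0.5, so 2 reductions.
- From 1.0 mg: 1.0 → 0.5, so 1 reduction. A further step gives 0.5 − 0.5 = 0.

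Two regimens remain in use. Full: 21 × 1 mg = 21 mg per cycle. Reduced: 10 × 1 mg = 10 mg per cycle, which is 10/21 = 47.6% of full, or 52.4% lower. The ceiling of two fits a 1.5 mg start, and Section 11.1 still names Dose Level 2 as the expected Phase 2 dose.

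**3. The diary sentence if followed literally.**

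- Intended by Day 10: doses on Days 1, 3, 5, 7 and 9 = 5 mg, or 5/10 = 0.5 mg/day.
- Taken daily by Day 10: 10 × 1 mg = 10 mg, or 1.0 mg/day. Ratio 10/5 = 2.
- The 10 capsules dispensed (Section 6.1) are then used up, so the cycle total stays at 10 mg.
- Pill-count compliance, by the diary's formula: (10 − 0)/10 × 100 = 100%. The count would not show the error. The diary would, because five entries (Days 2, 4, 6, 8 and 10) would fall in crossed-out boxes.

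**4. Error rates.** With n1 = 19 (stop at 9 or fewer) and n = 37 (promising at 24 or more), the probability of a positive conclusion is the sum over x = 10 to 19 of P(X1 = x) × P(X2 ≥ 24 − x), with X1 ~ Bin(19, p) and X2 ~ Bin(18, p). The exact calculation gives early-stopping probabilities of 50.0% at p = 0.50 and 3.3% at p = 0.70, as Section 11.2 states, with type I error 0.0487 and power 80.3%. No dosing rule enters these figures.

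**The case against.** The strongest defence is that the rules can be reconciled. Section 6.4 names the narrower class and decides whether treatment continues, while 6.2.4 decides the dose for those who do continue. On the usual reading that the specific rule governs, the conflicting row disappears. This is probably what was intended, but the protocol does not say so, and 6.2.4 uses mandatory wording without a cross-reference.

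A reader might infer that the plan lets Grade 4 hypertension resume at the same dose despite 6.4. The documents do not settle this. Table 3, 6.2.3 and 6.2.5 route hypertension through its own management first, and the content of Appendix C is not shown in the text available. The same-dose sentence also depends on the investigator's opinion of safety.

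On the number of reductions, a reader might infer that a reduced patient is left without any rule. That goes too far. Two is a ceiling, not an instruction to make two. For events other than hypertension, Table 3 and 6.2.3 allow resumption only at a lower level, and none is left. Section 3.3.3 treats until progression or toxicity, and 6.4 lists treatment-related toxicity, investigator judgment and interruptions beyond two weeks. What stands is that no text expressly says to stop when a further reduction is needed and the event resolves within two weeks.

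On the diary, a reader might infer a likely overdose. The numbered grid, the crossed-out days and the 10-capsule supply argue against it, and the daily dose would not exceed 1 mg, the dose found tolerated in Phase 1b. The sentence is still wrong for the schedule it accompanies. Diary text that also appears inside Section 7.11, and the open Day 21 box in the grid, may be artefacts of text extraction and carry no weight here.

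**Conclusion.** The point holds as a set of three drafting errors in current dosing text, with a limited effect on patient safety. They should be corrected.

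- The reduce-or-stop conflict affects only non-hematologic Grade 4 related events that do not meet the 6.4 exception. It rests mainly on 6.2.4, assuming that 6.2.1 is confined to Phase 1b.
- From 1 mg there is one reduction, against a stated ceiling of two. Existing provisions lean toward stopping afterwards but leave it to inference.
- The diary sentence, if followed, doubles the intended dose rate for up to 10 days (1.0 instead of 0.5 mg/day). This is unlikely, given the grid and the supply.

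The number of patients affected cannot be derived from the documents. A reader might infer that the inconsistencies weaken the 24-week PFS result. The documents show no such effect, and alpha, power and sample size are unchanged.

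**What to change.** 1. Make Sections 6.2.1 and 6.2.4 and the Grade 4 row of Table 3 expressly subject to Section 6.4. If 6.2.1 applies to Phase 1b only, say so. For hypertension, check the 6.2.4 wording against Appendix C before finalizing.
2. In 6.2.4, state that one reduction is allowed from 1 mg, to 1 mg every other day for 10 doses, and that toxicity requiring a further reduction leads to discontinuation.
3. In the dose-reduced diary, replace the daily instruction with: every other day, on the numbered dose days (Days 1, 3, ..., 19).

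The cost is a few text edits in one amendment and a reissued dose-reduced diary. There is no analysis or sample size cost.

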## **6.5 Compliance**

Patients will be instructed to record date for each day and the total number of pills taken each day (**Appendix E**). Dosing compliance will be monitored at each clinic visit. Phase 1b patients who do not complete at least 80% of the prescribed dose in Cycle 1 for reasons other than DLT will be replaced. Otherwise, if a patient has 2 consecutive cycles of less than 50% compliance, the patient will be deemed non-compliant and come off study. At the discretion of the investigator, if the patient is benefiting from the treatment the patient may continue on study. Patients who come off study, due to non-compliance, will not be replaced.

## **7 STUDY PROCEDURES**

### **7.1 Baseline Evaluations**

The following will be performed within 2 weeks prior to treatment start and prior to receiving any study-related procedures:

- Informed consent: Must be completed prior to receiving any study-related procedures.
- Medical history

- Physical examination, including vital signs (i.e., temperature, heart rate, respiratory rate, blood pressure, body weight, and height)
- Hematology (i.e., complete blood count (CBC) with differential, absolute neutrophil count (ANC), and platelets)
- Chemistry (comprehensive metabolic panel (i.e., AST, ALT, total bilirubin, alkaline phosphatase, creatinine, potassium, glucose, and calcium) and serum albumin.
- Alpha-Fetoprotein (AFP)
- PT/INR
- Urine pregnancy test in females of childbearing potential (performed within 1 week prior to treatment start).
- ECOG Performance Status
- Electrocardiogram
- CT Scan- (within 4 weeks)
- Concomitant Medications (Any ongoing medications with an onset within 1 week of first dose of study drug.)
- Hep B and C testing (if unknown). Blood collection of about 4 teaspoons will be drawn from your arm for HBsAg, (the surface antigen of the hepatitis B virus (HBV). And Hep C Ab with verification.
- Urine will be collected to calculate urine protein and creatinine ratio.

## **7.2 Evaluations Performed at Cycle 1, Day 1**

- Physical examination, including vital signs (i.e., temperature, heart rate, respiratory rate, blood pressure, and body weight)
- Hematology (i.e., CBC with differential, ANC, and platelets)
- Chemistry (comprehensive metabolic panel (i.e., AST, ALT, total bilirubin, alkaline phosphatase, creatinine, potassium, glucose, and calcium) and serum albumin.
- PT/INR
- Pharmacokinetic/Pharmacodynamic sVEGF-2 Sampling
- Immune Biomarker Sampling
- ECOG Performance Status
- Tivozanib (Patients will be administered tivozanib in clinic following their pre-dose pharmacokinetic/pharmacodynamic sample).
- Concomitant Medications
- If either (or both) HBsAg or Hep C Ab with verification are positive, blood will be collected for viral load anytime pre-treatment. (Viral load test: Hep B (or C) virus PCR, Quant).

**7.3 Evaluations Performed at Cycle 1, Day 15 ( $\pm$  3 Days)**

- Physical examination, including vital signs (i.e., temperature, heart rate, respiratory rate, blood pressure, and body weight)
- Hematology (i.e., CBC with differential, ANC, and platelets)
- Chemistry (comprehensive metabolic panel (i.e., AST, ALT, total bilirubin, alkaline phosphatase, creatinine, potassium, glucose, and calcium) and serum albumin.
- PT/INR
- Pharmacokinetic/Pharmacodynamic sVEGF-2 Sampling
- ECOG Performance Status
- Tivozanib (Patients will be administered tivozanib in clinic following their pre-dose pharmacokinetic/pharmacodynamic sample).
- Concomitant Medications
- Adverse Events

**7.4 Evaluations Performed at Day 1 of Each Cycle After Cycle 1 ( $\pm$  3 Days)**

- Physical examination, including vital signs (i.e., temperature, heart rate, respiratory rate, blood pressure, and body weight)
- Hematology (i.e., complete blood count (CBC) with differential, absolute neutrophil count (ANC), and platelets)
- Chemistry (comprehensive metabolic panel (i.e., AST, ALT, total bilirubin, alkaline phosphatase, creatinine, potassium, glucose, and calcium) and serum albumin.
- PT/INR
- ECOG Performance Status
- Tivozanib (Patients will take at home).
- Concomitant Medications
- Adverse Events
- Alpha Fetoprotein (AFP): Biomarker to detect hepatocellular cancer every 2 cycles, starts with cycle 3 (Only if elevated at baseline).
- A computed tomography scan (CT scan) every 2 cycles, not to exceed 10 weeks apart.
- Urine will be collected to look at protein and creatinine levels every 2 cycles starting with cycle 3
- If either (or both) HBsAg or Hep C Ab with verification are positive, blood will be collected for viral load, (Hep B (or C) virus PCR, Quant) every 2 cycles starting with cycle 3

**7.5 Evaluations Performed at Cycle 3, Day 1 ( $\pm$  3 Days)**

- Physical examination, including vital signs (i.e., temperature, heart rate, respiratory rate, blood pressure, and body weight)
- Hematology (i.e., CBC with differential, ANC, and platelets)
- Chemistry (comprehensive metabolic panel (i.e., AST, ALT, total bilirubin, alkaline phosphatase, creatinine, potassium, glucose, and calcium) and serum albumin.
- ECOG Performance Status
- AFP (Only test if AFP was elevated at baseline).
- PT/INR
- Immune Biomarker Sampling
- CT Scan
- Concomitant Medications
- Adverse Events
- Urine will be collected to look at protein and creatinine levels every 2 cycles starting with cycle 3
- If either (or both) HBsAg or Hep C Ab with verification are positive, blood will be collected for viral load. (Viral load test: Hep B (or C) virus PCR, Quant)

**7.6 Evaluations Performed at 1 Year ( $\pm$  7 Days)**

- Immune Biomarker Sampling (When the patient progresses/comes off study drug or at 1 year whichever occurs first.)

**7.7 Evaluations Performed at End of Treatment**

- Physical examination, including vital signs (i.e., temperature, heart rate, respiratory rate, blood pressure, and body weight)
- Hematology (i.e., CBC with differential, ANC, and platelets)
- Chemistry (comprehensive metabolic panel (i.e., AST, ALT, total bilirubin, alkaline phosphatase, creatinine, potassium, glucose, and calcium) and serum albumin.
- CT Scan (Only if last CT scan was more than 28 days prior to end of treatment.)
- PT/INR
- Immune Biomarker Sampling (When the patient progresses/comes off study drug or at 1 year whichever occurs first.)
- ECOG Performance Status
- Concomitant Medications

- Adverse Events

**7.8 Follow-Up: Medical Record review every 6 months for overall survival.**

**7.9 Schedule of Procedures and Observations**

The schedule of procedures and observations for this study is summarized in **Table 4** below.

**Table 4. Schedule of Procedures and Observations**

Evaluation	Baseline	Cycle 1 Day 1	Cycle 1 Day 15 (± 3 days)	Day 1 of Each Cycle After Cycle 1 (± 3 days)	Cycle 3 Day 1 (± 3 days)	1 Year (± 7 days)	End of Treatment
Informed Consent	X						
Medical History	X 						
Physical Examination , including vital signs (i.e., temperature, heart rate, respiratory rate, blood pressure, body weight, and height)	X 	X	X	X	X		X
Hematology	X 	X	X	X	X		X
Chemistry	X 	X	X	X	X		X
HBsAg	X						
Hep C Ab With Verification	X						
Viral Load (Hep B(or C) virus PCR, Quant)		X 		X 	X 		
Alpha-Fetoprotein (AFP)	X 			X 	X 		
PT/INR	X 	X	X	X	X		X
Pharmacokinetic/Pharmacodynamic and sVEGF-2 Sample Collection		X 	X 				
Immune Biomarker Sample Collection		X 			X 	X 	X 
Pregnancy Test (Urine)	X 						
Urine Protein/Creatinine ratio	X 			X 	X 		
ECOG Performance Status	X 	X	X	X	X		X
Electrocardiogram	X 						
CT Scan	X 			X 	X 		X 
Tivozanib		X 	X 	X			

Evaluation	Baseline	Cycle 1 Day 1	Cycle 1 Day 15 (± 3 days)	Day 1 of Each Cycle After Cycle 1 (± 3 days)	Cycle 3 Day 1 (± 3 days)	1 Year (± 7 days)	End of Treatment
Concomitant Medications	X 	X	X	X	X		X
Adverse Events			X	X	X		X

1 Performed within 2 weeks prior to treatment start and prior to receiving any study-related procedures.
 
2 Height collected at baseline only.
 
3 Hematology (i.e., complete blood count (CBC) with differential, absolute neutrophil count (ANC), and platelets).
 
4 Chemistry (comprehensive metabolic panel (i.e.; AST, ALT, total bilirubin, alkaline phosphatase, creatinine, potassium, glucose, and calcium) and serum albumin).
 
5 Only test if AFP was elevated at baseline.
 
6 Refer to Section 7.10.
 
7 Pre-dosed cycle 1 day 1, cycle 3 day 1, when the patient progresses/comes off study drug or at 1 year whichever occurs first. Refer to Section 7.11.
 
8 Performed within 1 week prior to treatment start.
 
9 Only if last CT scan was more than 28 days prior to end of treatment.
 
10 Patients will be administered tivozanib in clinic following their pre-dose pharmacokinetic/pharmacodynamic sample.
 
11 Medications ongoing within 1 week prior to first dose of study drug.
 
12 CT every 2 cycles starting with cycle 3, with maximum of 10 weeks apart.
 
13 Collect viral load, pre-treatment, if either (or both) HBsAg or Hep C Ab with verification are positive & every 2 cycles starting with cycle 3.
 
14 Every 2 cycles starting with cycle 3.
 
15 Patients will be followed for overall survival, every 6 months by medical record review
 
16 CT scan within 4 weeks prior to treatment start.
 
17 Only if unknown
							

